5.4. GROUPS OF CONTROLS

To facilitate the analysis, several groups of controls will be defined. It is acknowledged that data for the vast majority of subjects in the controls will represent a shorter duration than seen in subjects within OLE Gant All Gant exposure mITT.

5.4.1. EXTERNAL CONTROLS

External control subjects will be identified by [REDACTED] and approved by Washington University from the associated DIAN-OBS data freeze (DF16 for both the interim analysis and the final analysis) based on matched DIAN-TU inclusion/exclusion criteria used to select external controls as described in Section 7.2 of the double-blind SAP (including the use of Appendix II and Section 12.1.2 in that SAP to calculate EYO), with the exceptions of CDR Global being used rather than components of the DIAN-MCE and some variable selections in [Table A](#) below

[REDACTED] [REDACTED]

Author: [REDACTED]	Version Number:	7
	Version Date:	07Dec2023

Template No.: CS_TP_BS016 Revision 6 Reference: CS_WI_BS005
 Effective Date: 02Dec2019

differing from those used in the double-blind SAP. The exception to the convention is that subjects already selected for double-blind period as Eligible DIAN-OBS subjects will be retained with the same baseline visit as identified in the double-blind selection.

[REDACTED] [REDACTED]

Author: [REDACTED]

Version Number: 7

Version Date: 07Dec2023

Template No.: CS_TP_BS016 Revision 6

Reference: CS_WI_BS005

Effective Date: 02Dec2019

Table A: DIAN-TU-001 Exclusion Criteria Specified in Protocol Amendment 10 That Can Be Validated Using Information from the DIAN-OBS Database

DIAN-TU-001 Exclusion Criteria	Corresponding DIAN-OBS Available Information	DIAN-OBS Data Source	Variable Names in DIAN-OBS (the values to remove)
4.2.3	Subjects with recent health history of stroke, cerebral hemorrhage or transient ischemic attack.	UDS Form A5 Subject Health History (Item 2a/2b)	CBSTROKE (1) CBTIA (1) Eligibility Baseline MCH (5+)
4.2.4	Subjects with alcohol or drug dependence sufficient to meet DSM-IV criteria currently or within the past 1 year.	UDS Form A5 Subject Health History (Item 7a,7c)	ALCOHOL (1) ABUSOTHR (1)
4.2.6, 7, 8, 9, 10	Subjects with recent myocardial ischemic events, congestive heart failure or major cardiovascular procedures including angioplasty / endarterectomy/stent, cardiac bypass procedure, pacemaker	UDS Form A5 Subject Health History (Item 1a,1c,1d,1e,1f)	CVANGIO (1) CVBYPASS (1) CVCHF (1) CVHATT (1) CVPACE (1)
4.2.3, 11	Subjects with active atrial fibrillation or in treatment with anticoagulation	UDS Form A4 Subject Medications UDS Form A5 Subject Health History (Item 1b)	DRUGID (d00210 d00022) CVAFIB (1)
4.2.18	Subjects with clinically significant deficiency in B12 (recent diagnosis or in active treatment)	UDS Form Neurological Exam (Item 8, 9) UDS Form A5 Subject Health History (Item 5d)	NXSENSOR (2) and NXTENDON (2) and B12DEF (1)

Author: [REDACTED]

Version Number:

7

Version Date:

07Dec2023

Template No.: CS_TP_BS016 Revision 6

Reference: CS_WI_BS005

Effective Date: 02Dec2019

When subjects meet the criteria above (per the respective DIAN-OBS data freeze corresponding to the analysis) to be included in the DIAN-TU-001 primary analysis, selected secondary, and selected sensitivity analyses, only their data from the point of eligibility and thereafter will be included.

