Further, this platform study design allows for flexibility and for the application of an “adaptive design” for which study drug is used. For example, if a study drug failed early due to adverse events or lack of efficacy, a new compound could be added to the same protocol and new participants could be randomized to the actively enrolling study drug arms or a CRI period may open for recruitment.

A more traditional study design with separate biomarker and cognitive endpoints would be extremely difficult in this cohort for two reasons: 1) The participant pool is very limited as families with DIAD causing mutations are rare; and 2) A prolonged treatment period (≥ 4 years in this study) may be needed to determine if the study drugs can slow or prevent cognitive changes in an asymptomatic cohort. The inclusion of these cognitively normal participants is very important, as they may be most likely to benefit from disease-modifying treatments.

However, the subtle cognitive change in the asymptomatic mutation carriers limits the power to detect treatment effects when there are small numbers of participants enrolled. One method to improve the power to detect treatment effects is to include additional control participants. The DIAN Observational study (DIAN-OBS) has been following nearly the same protocol as DIAN-TU-001 to study the natural history of disease progression in DIAD. Given the similarities of the protocol and the fact that the DIAN-OBS study has contributed a significant proportion of the participants to the DIAN-TU-001, data will continue to be used from DIAN-OBS participants who meet the inclusion criteria for DIAN-TU-001 to track disease progression, regardless of the specific therapy being tested. The DIAN-OBS data will be used as additional control participants and will be utilized as a control group to improve power.

Cognitive Run-in Period to Establish Trial-Ready Cohort

A CRI period may be opened prior to randomization into drug arms added to the platform trial. To determine the potential benefits for statistical power, a detailed simulation analyses was

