3.4 Participant Enrollment and Randomization

Participants will be recruited from or may be referred to a DIAN-TU site for screening. The complexity of the study and the likelihood that many participants may live at a distance from the DIAN-TU site create additional challenges for enrollment. Individuals interested in the study will be provided with an informed consent form (ICF) for review.

The participant's personal information will be used to create the Globally Unique Identifier (GUID), which consists of random characters. Once the GUID is created, qualified researchers can use it to link an individual's research data across studies, including DIAN-OBS, DIAN-EXR and future studies, without using identifying personal information.

If more than one study drug arm is enrolling, a main ICF will provide detailed information on study design, number and timing of visits and procedures, and the rationale for use of drugs targeting AD pathology. The main ICF will provide information on the route of administration, potential side effects associated with drugs that target A β or tau, and study procedures. The ICF will explain that participants will be assigned randomly to an eligible study drug arm and if more than one of the study drug arms is recruiting simultaneously, they will not be able to

choose a specific study drug arm. If only one drug is enrolling, one ICF may be utilized. Local regulations and ethics committee requirements must be followed and may require alternate consent structure and/or practices.

For participants enrolling into the CRI period, an ICF specific to the CRI period will be used. The CRI ICF will provide detailed information on study design, duration, number and timing of visits, procedures, and potential side effects associated with drugs that target amyloid-beta or tau, and intent for participants to enroll in a study drug arm when one becomes available. It will also include the main requirements of future potential drug arm(s) (e.g., duration and frequency of procedures). The CRI ICF will explain that participants who continue to meet eligibility criteria may be randomized to a study drug arm once a drug arm is open. The ICF should be clear that there is the potential to be excluded from the study drug arm if any entry criteria are not met, and it is in the best interest of the participant not to participate.

Participants will be re-consented prior to randomization to a study drug arm.

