19. Current clinically significant abnormalities of thyroid function studies, clinically significant deficiency in B₁₂. B₁₂ less than the lower limits of normal with normal methylmalonic acid (MMA)/homocysteine is not deemed clinically significant, therefore not exclusionary⁴.
20. HbA1c >8% (retesting is permitted if slightly elevated) or poorly controlled insulin-dependent diabetes (including hypoglycemic episodes). Participants may be rescreened after 3 months to allow optimization of diabetic control.
21. Morbid obesity with significant comorbidities or that would preclude MRI imaging.

Co-Medications

22. Current chronic use of anticoagulants (e.g., warfarin, dabigatran, rivaroxaban or apixaban) or of clopidogrel is exclusionary. Limited (occasional or isolated) use of anticoagulants / antiplatelet compounds in cases such as surgical procedures, as well as daily use of low dose (\leq 325 mg) aspirin is not exclusionary.
23. Have been exposed to a monoclonal antibody targeting beta amyloid peptide within the past six months, or five half-lives from screening visit (V1), whichever is longer.
24. Received any other investigational treatment within 3 months or 5 half-lives of CRI Screen and screening visit (V1), whichever is longer.

Note: Use of some treatments for AD and other medications may be permitted in this study in accordance with the guidelines in Concomitant Medications, Section 5.3.

Other

25. Lack of sufficient venous access.
26. Clinically relevant abnormalities in hematology, coagulation studies or clinical chemistry.
27. History of cancer within the last 5 years, except basal cell carcinoma, non-squamous skin carcinoma, prostate cancer or carcinoma in situ with no significant progression over the past 2 years.
28. Any other medical condition that could be expected to progress, recur, or change to such an extent that it could bias the assessment of the clinical or mental status of the participant to a significant degree or put the participant at special risk.

⁴ If B₁₂ is less than the lower limits of normal, a follow-up test of MMA and/or homocysteine should be performed to assess MMA/homocysteine

29. Currently, or within the last month prior to CRI Screen or screening (V1), participated in a clinical trial including a nonpharmacological trial with a key objective of improving cognition.
30. Positive urine or serum pregnancy test or plans or desires to become pregnant during the course of the trial.

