The same analysis will also be applied to the OLE Gant All Gant exposure mITT population and the All Gant exposure mITT populations, along with all controls. This model will be tested using linear splines, which fits two slopes with one prior to the OLE baseline and one after the OLE

Author:	[REDACTED]	Version Number:	7
	[REDACTED]	Version Date:	07Dec2023
Template No.:	CS_TP_BS016 Revision 6	Reference:	CS_WI_BS005
Effective Date:	02Dec2019		

Copyright © 2009, 2010, 2012, 2016, 2018, 2019 [REDACTED] All rights reserved. The contents of this document are confidential and proprietary to [REDACTED] Holdings Inc. and its subsidiaries. Unauthorized use, disclosure or reproduction is strictly prohibited.

baseline (the linear splines have a node at the OLE baseline) to account for the different dosing regimens in the DIAN-TU-001 gantenerumab exposure population; for the pooled controls, only one slope will be fitted since no treatment was administered at any point in time. The analysis will also be conducted for each population based on the baseline asymptomatic and symptomatic subjects presented separately.

Figures of model estimated mean over time by treatment arms or spaghetti plots of individual data over time/EYO by treatment arms will be presented as deemed necessary by Washington University team and may be included in CSR as needed. The plots will also be presented separately for baseline asymptomatic and symptomatic subjects at the OLE baseline.

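### SAP 5.4.1 states no anti-amyloid or investigational-treatment exclusion for external controls and no cut-off at drug start or trial entry, yet Section 16.2.3.3 treats the controls as untreated throughout

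*SAP*

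**What the plan says.** SAP Section 5.4.1 draws external controls from DIAN-OBS data freeze DF16, "based on matched DIAN-TU inclusion/exclusion criteria used to select external controls as described in Section 7.2 of the double-blind SAP", with a few stated departures. Table A is headed as covering the "Exclusion Criteria Specified in Protocol Amendment 10 That Can Be Validated Using Information from the DIAN-OBS Database". Its rows deal with stroke, TIA and microhemorrhage; alcohol or drug dependence; cardiac events and procedures; atrial fibrillation or anticoagulation; and B12 deficiency.

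Once a person qualifies, "only their data from the point of eligibility and thereafter will be included". For people chosen earlier, "subjects already selected for double-blind period as Eligible DIAN-OBS subjects will be retained with the same baseline visit".

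Section 5.4.3 adds these controls to the double-blind placebo participants who did not enter the extension, forming the main set controls. In the spline version of the mixed model in Section 16.2.3.3, "only one slope will be fitted since no treatment was administered at any point in time" for the pooled controls.

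**The concern.** Protocol Section 4.2 excludes trial candidates who "Have been exposed to a monoclonal antibody targeting beta amyloid peptide within the past six months" (or five half-lives, if longer) and those recently given another investigational treatment. Neither criterion appears in Table A, and no rule in this SAP ends a control's data when such treatment starts.

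The route to exposure is plausible. Protocol Section 3.2 says that "the DIAN-OBS study has contributed a significant proportion of the participants to the DIAN-TU-001". The platform also ran solanezumab and atabecestat arms, and Protocol Section 5.3 names an approved anti-amyloid drug. Under SAP Section 5.4.5, concurrent external controls are those who become eligible on or after the first double-blind dose, so their follow-up falls in that period.

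Two things are at stake. Follow-up on a drug could be counted as untreated progression. The same person could also supply control records from DIAN-OBS and treated records from the trial, which the models would take as two independent subjects.

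**Working it through.** **1. Where the controls' data can end.** I read every SAP rule on control baseline, data inclusion and censoring: Sections 5.4.1 to 5.4.6, 6.1, 6.2.2, 7.1, 16.2.3.1 to 16.2.3.3, 16.2.4 and 17.

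- Start: the point of eligibility (5.4.1).
- End: the DF16 freeze (5.4.1) and, in the Cox models, censoring at the last measurement (16.2.3.1 and 16.2.3.2). Section 16.2.3.1 applies its event definition to all controls.
- End at first drug dose or at trial entry: none stated.

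**2. What screens for treatment.** Table A has no such row. It does use DIAN-OBS medication Form A4, but only for two drug codes in the atrial fibrillation and anticoagulation row.

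**3. What a screening exclusion could do.** Both protocol exclusions look back from screening (six months, three months, or five half-lives). Applied at eligibility, they remove earlier exposure. They do not reach exposure that starts later.

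**4. Which analyses use external controls.**

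| Analysis | External controls? |
|---|---|
| PiB-PET primary (16.1.3) | No controls |
| CDR-SB recurrent-event Cox (16.2.3.1) | Yes; also an interim primary analysis (17) |
| CDR Global Cox (16.2.3.2) | Yes; also an interim primary analysis (17) |
| Mixed models for cognitive composite, FAS, MMSE, CSF NfL and MTBR243 (16.2.3.3) | Yes |
| Tau-PET mixed model (16.2.3.3) | Internal only |
| MMRM analyses (5.4.6, 16.2.3.4, 16.2.3.5) | Internal only, or none |

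**5. Illustrative size.** The plan gives no figure to reproduce. The number of external controls, their person-time and any exposure are not in the documents. Let h be the true hazard ratio of gantenerumab against untreated controls, p the share of control risk time on a drug, and g that drug's own hazard ratio. The average control hazard is then multiplied by (1 − p + p·g), so

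observed HR = h / (1 − p + p·g).

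Assume g = h, meaning the controls' drug works as well as gantenerumab and does so at once:

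| p | h = 0.50 | h = 0.70 |
|---|---|---|
| 5% | 0.50/0.975 = 0.51 | 0.70/0.985 = 0.71 |
| 10% | 0.50/0.950 = 0.53 | 0.70/0.970 = 0.72 |
| 20% | 0.50/0.900 = 0.56 | 0.70/0.940 = 0.74 (0.745) |
| 30% | 0.50/0.850 = 0.59 | 0.70/0.910 = 0.77 |

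If g is below 1, the denominator is below 1 and a benefit is understated. If g is above 1, the denominator exceeds 1 and a benefit is overstated. If g = 1, there is no bias from exposure.

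**The case against.** The best defence is that selection does not rest on Table A alone. Section 5.4.1 imports Section 7.2 of the double-blind SAP, and anything there on treatment or truncation would carry over unless it is one of the stated departures. By its own title, Table A lists only what DIAN-OBS data can verify, so a missing row may reflect what was recorded. This stands. A reader might infer that the plan never screens controls for treatment, but without Section 7.2 and Protocol Amendment 10 that cannot be said, only that this SAP does not state it.

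Nor is follow-up unlimited: DF16 and the last measurement are administrative ends. What is missing is an end linked to treatment or trial entry.

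A reader might also infer that retained controls were screened before their later follow-up accrued. The double-blind freeze is not dated in the documents, so that timing is unsupported. The retention rule fixes membership and baseline and is silent on re-checking.

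It is tempting, too, to conclude that a gantenerumab effect would be hidden. The documents do not fix the direction. Protocol Section 1.4 reports cognitive impairment with BACE inhibitors, a class tested on this platform, which in controls would favour gantenerumab.

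Finally, no document shows that any control was exposed, or that people who joined the trial kept contributing DIAN-OBS visits. The SAP's version history says the extension ended early with no path to approval, which lowers the stakes. None of this supplies the missing stop.

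**Conclusion.** The point holds in a limited form. As written, this SAP would count follow-up after drug start or trial entry as untreated control data, and its spline model relies on that never happening. The gap bears on the CDR-SB and CDR Global comparisons, including the two interim primaries, and on the mixed models that use external controls. The primary PiB-PET conclusion is untouched.

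The size is unknown. Under the equal-effect assumption, 5 to 10% exposed time moves the hazard ratio by only 0.01 to 0.03, and 30% moves it by 0.07 to 0.09. These are conditional illustrations and not estimates for this trial; with a harmful drug the shift would be in the other direction. The conclusion would fall away if Section 7.2 of the double-blind SAP already truncates control data at exposure and trial entry and that rule applies to the DF16 follow-up.

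**What to change.** Add to Section 5.4.1:

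> External controls, including those retained from the double-blind selection, must meet the trial's anti-amyloid-antibody and investigational-treatment exclusions at the point of eligibility. Their data are censored at the first known dose of any anti-amyloid or investigational AD drug, or at enrolment in any DIAN-TU treatment arm or other interventional AD drug trial, whichever is first.

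Cite the exclusions by content, because numbering differs between amendments: B12 deficiency is 4.2.18 in Table A (Amendment 10) but item 19 in the supplied protocol. If Section 7.2 already contains these rules, cite it here and confirm that it covers follow-up after the double-blind selection.

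Identify exposure from DIAN-OBS medication data where recorded; whether Form A4 captures investigational or blinded drug needs checking. Identify trial entry through the GUID: Protocol Section 3.4 says "qualified researchers can use it to link an individual's research data across studies, including DIAN-OBS".

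Censoring at enrolment does not remove within-person dependence. Anyone who supplies both control and trial data should keep one linked ID in the robust variance or random effects, or be dropped from the external controls in a sensitivity analysis. Section 16.2.3.2 names no robust variance, so the CDR Global model would need one. For the interim, already run according to the version history, this can only be a labelled re-analysis.

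The cost is the added wording, one linkage and medication check, and some lost control follow-up. Report the number of controls and the person-time removed.

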5.4.2. INTERNAL SET CONTROLS

The internal set controls are defined as the placebo data from the double-blind period among subjects who did not enter the open-label extension.

5.4.3. MAIN SET CONTROLS

The main set controls are defined as the external controls plus the internal set controls.

5.4.4. EXTENDED SET CONTROLS

The extended set controls are defined as the main set controls plus the double-blind baseline and OLE baseline values for subjects treated with placebo during the double-blind period who entered the OLE. This set will be an additional set used with the OLE Gant All Gant exposure mITT to add further long-term follow-up given that the two timepoints will differ by over four years for subjects added to this control group.

